Single 24-hour urine collection	Collect within 14 days prior to dosing (M3) or visit (M4, M5, M6); repeat if invalid. See Table 4			х	х	Х	Х			
Blood sample for PD analyses	Section 6.3	X	X	X			X	X	X	
Clinical laboratory assessments	Section 6.5.4	X	X	X			X	X	X	X
Antidrug antibody sample	Section 6.5.4.1		X	X			X	X	X	X
Urine pregnancy test (for WOCBP) c	May be performed more frequently where required per local requirements, or if pregnancy is suspected. See Section 6.5.4.2		х	X				Х		
Symptom-directed physical examination	Section 6.5.3		X	X				X		X
Prior and concomitant medications	Section 5.4		Continuous							

Table 1: Schedule of Assessments

			1	5 Monti Treati	h Doub nent Pe		I			
		Screening	Pri	mary A	nalysis l	Period		Treat Exter Per	nsion	Safety
Study Visit			Baseline	М3	M4	MS	М6	ЕОТ М9	EOS/ ET M15	Follow-up (Patients who D/C Treatment Early)
Study Day (±Visit Window)	Notes	-60 to -1	Day 1	85 (±14)	113 (±7)	(41 (±7)	169 (±14)	253 (±28)	421 (±28)	3 and 6 months post last dose (±28)
Clinical kidney stone events	Section 6.2.2				C	ontinuo	us			
Review/record adverse events	Section 6.5.5				C	ontinuo	us			
Healthcare utilization	Section 6.6				C	ontinuo	us			
Randomization	Window: 1 business day prior to Day 1 for study drug preparation		X							
Blood samples for PK analyses	Table 2; Section 6.4		X							
Study drug administration	Section 5.2.2		X	X				X		
Optional low-dose kidney- protocol CT scan d	Section 6.2.2.2		X (-3 days window)			1 64			X	

Abbreviations: CT=computed tomography; D/C=discontinue; ET=early termination; EOS=end of study; EOT=end of treatment; M=month; PD=pharmacodynamic; PK=pharmacokinetic; WOCBP=women of child-bearing potential Notes:

- When scheduled at the same time points, assessments of vital signs should be performed before physical examinations and blood sample collections, where feasible.
- Patients who discontinue study drug dosing for any reason will be encouraged to remain on the study to complete the remaining assessments so that their experience is captured in the final analyses (refer to Section 4.3.1).

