- White columns indicate visits to the clinical study center; gray-shaded columns indicate study visits that may be conducted by a home healthcare professional, where applicable country and local regulations and infrastructure allow (at the discretion and with oversight of the Investigator, based on safety and tolerability), provided (for dosing visits) that the patient has tolerated a dose of lumasiran administered in the clinic. If a visit is conducted offsite, a body system assessment may be performed in lieu of a symptom-directed physical examination.
- In situations where a study visit is unable to be completed (either at the site or offsite by a healthcare professional), the Investigator (or delegate) will verbally contact the patient within the study visit window to assess concomitant medications, kidney stone events, and adverse events.

Footnotes:

- a All assessments are required to be performed prior to dosing at dosing visits, except for the PK 2-hour postdose sample collection and optional CT scan.
- b Inclusion/exclusion criteria should be verified prior to randomization. Laboratory assessments conducted to confirm study eligibility will not be repeated unless the time between screening and randomization exceeds 4 weeks.
- c Pregnancy test results must be known prior to dosing, if applicable.
- d Patients who elect to participate in optional CT scans will be requested to complete CT scans at both baseline (may be performed up to 3 days prior to Day 1), and at Month 15. The CT scans may be performed after dosing, if required.

Alnylam Pharmaceuticals Confidential 12

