# 3.3. Justification for Dose

Two dose levels of lumasiran 284 and 567 mg given on Day 1, Month 3, and Month 9 were selected to evaluate urinary oxalate dose response. The higher dose level of 567 mg is expected to suppress GO enzyme by ≥95%, comparable to the regimen evaluated in ALN-GO1-003 (ILLUMINATE-A) in patients with PH1. The lower dose of 284 mg is expected to suppress GO enzyme by 90%. In addition, the fixed doses will simplify dose administration in this adult study population. Both regimens are predicted to achieve near-steady state ribonucleic acid-induced silencing complex (RISC) concentrations and urinary oxalate suppression at Month 6. Month 9 dosing is intended to sustain PD effect through Month 15 and will provide data to differentiate the effect of every 3 months and every 6 months dosing on urinary oxalate reduction.

Single 0.3 to 6.0 mg/kg doses of lumasiran in healthy subjects and multiple 3.0 mg/kg doses of lumasiran administered monthly or once every 3 months in patients with PH1 have been well tolerated. Plasma and liver exposure for the lumasiran 284 and 567 mg doses are expected to be in the range of 3.0 to 6.0 mg/kg lumasiran doses evaluated in healthy subjects in ALN-GO1-001 (Part A) and patients with PH1 in ALN-GO1-001 (Part B), ALN-GO1-002, and ILLUMINATE-A. Based on rat and monkey NOAEL doses of lumasiran 200 mg/kg and 300 mg/kg, a sufficient safety margin exists for the use of lumasiran 284 and 567 mg doses (refer to the ALN-GO1 Investigator Brochure).

Based on a 70 kg patient, the planned doses of 284 mg and 567 mg equate to approximately 4.0 mg/kg or 8.0 mg/kg, respectively. The human equivalent dose (HED) margin values for the

approximate 4 mg/kg clinical dose were 8.1-fold for the chronic rat study and 24.2-fold for the chronic monkey study; the HED margin values for the approximate 8.0 mg/kg clinical dose were 4.0-fold for the chronic rat study and 12.1-fold for the chronic monkey study (refer to the ALN-GO1 Investigator Brochure).

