### **5.2.2.** Dose and Administration

Patients will be administered SC injections of lumasiran (284 mg or 567 mg) and/or placebo at the same volume, as described below, on Day 1, Month 3, and Month 9.

Lumasiran 567 mg	Lumasiran 284 mg	Placebo
1.5 mL lumasiran	1.5 mL lumasiran	1.5 mL placebo
1.5 mL lumasiran	1.5 mL placebo	1.5 mL placebo

Study drug injections will be administered under the supervision of the Investigator or healthcare professional. To maintain the blind, syringes are to be masked prior to the removal of study drug from vials. A full description of the blinding procedure is included in the Pharmacy Manual. The injection site may be marked and mapped for later observation. Injections may be administered in the abdomen, thigh, or the side or back of the upper arms. If a local reaction around the injection site occurs, photographs may be obtained. Detailed instructions for study drug administration are found in the Pharmacy Manual.

Dosing will be permitted at a location other than the study center (for example, the patient's home) by a healthcare professional with the oversight of the Investigator, provided the patient has tolerated at least 1 dose of study drug administered in the clinic. However, continued study

drug administration at the study center should be considered for patients who have ongoing study drug-related AEs or for anyone in the opinion of the Investigator who would benefit from clinical observation following dosing.

If a patient does not receive a dose of study drug within the specified visit window, the Investigator should contact the Medical Monitor. After such consultation, the dose may be administered or considered missed and not administered.

Additional details can be found in the Pharmacy Manual.

The definition of study drug overdose, follow-up procedures, and reporting requirements are provided Section 6.5.5.8.

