#### 6.2.1. 24-Hour Urine Collections

Urinary oxalate excretion and calcium oxalate supersaturation (calculated from multiple parameters) will be determined from 24-hour urine sample collections to be completed at the time points specified in the Schedule of Assessment (Table 1). The start and stop dates/times of collection, the volume of urine in the collection, whether there were any missed voids, and whether the patient complied with dietary recommendations will be recorded. An aliquot of the 24-hour urine collection will also be used to determine urinary creatinine content and to determine if the 24-hour urine collections need to be repeated (see Section 6.2.1.1).

The 24-hour urine collection procedure by study visit is provided in Table 4.

Table 4: 24-hour Urine Collection Procedure by Study Visit

Study Visit and Urine Collection Window	Number of Collections to Schedule	Validity Requirement Prior to Dosing/Visit (see Section 6.2.1.1)	Notes
Screening (within 60-day period)	2	2 valid collections prior to dosing unless variability criterion is not met (Section 6.2.1.2), in which case an additional collection is required a .	Supervised collections b are encouraged unless patient is already familiar with the collection procedure. If any collections are invalid, the remaining collections for screening must be supervised.
Months 3, 4, 5, and 6 (within 14 days prior to dosing/visit)	1	No	If an invalid collection is obtained for the timepoint, a single repeat collection must be supervised. Repeat collection, if necessary, is to be completed within ±14 days of dosing/visit.
Months 9 and 15 (within 14 days prior to dosing/visit)	2	1 valid collection prior to dosing/visit	If a patient has had ≥2 prior invalid collections, both collections at these visits must be supervised b . At least 1 valid collection must be obtained prior to dosing/visit. If any collections for the timepoint are invalid, the remaining collection(s) for the timepoint must be supervised.

<sup>a The additional collection is not required to be valid in order to proceed with dosing, but will be tested to confirm validity for the calculation of baseline 24-hour urinary oxalate.

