## 6.3. Pharmacodynamic Assessments

Urine and blood samples will be collected for assessment of PD parameters (plasma oxalate and plasma glycolate, and 24-hour urinary glycolate) at the time points specified in the Schedule of Assessments (Table 1). On dosing days, all blood and urine samples will be collected prior to study drug administration.

All PD assessments will be analyzed centrally. Postdose PD results will not be distributed to the sites until after the last patient completes assessments at the Month 15 visit. Site personnel should refrain from obtaining or viewing local oxalate, calcium oxalate supersaturation, or glycolate assessments, except as medically indicated, due to risk of unblinding (Section 3.5). Details regarding the processing and aliquoting of PD samples for shipping and storage are provided in the Laboratory Manual.

Where local regulations allow and infrastructure is in place, a healthcare professional may collect urine or blood samples offsite.

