4.7. Visit Windows

For PD and safety parameters, no window rules will be implemented, and the reported eCRF visits will be used for analysis.

The following general conventions for unscheduled assessments will apply unless otherwise specified:

- If by-visit summaries are based on CRF Visit, only scheduled assessments will be included in by-visit summaries. Unscheduled assessments will not be included.
- Unscheduled assessments will be used in the calculation of baseline values and for shift from baseline to worst post-baseline tables. They will also be included in by-patient listings and spaghetti plots.

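### Table 4 lets a Month 3 repeat urine be taken up to 14 days after the Month 3 dose, and the SAP has no timing rule to stop it being analysed as the Month 3 value

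*Protocol*

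**What the plan says.** Protocol Table 1 sets visits as study days counted from the first dose. The Month 3 dosing visit is Day 85 ±14 and the Month 4 visit is Day 113 ±7. No text moves the Month 4 visit when the Month 3 dose is early or late. Under Protocol 5.2.2 a dose that misses its window goes to consultation, and "After such consultation, the dose may be administered or considered missed and not administered".

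The first urine collection is tied to dosing at Month 3 and to the visit at Months 4 to 6: "Collect within 14 days prior to dosing (M3) or visit (M4, M5, M6); repeat if invalid" (Table 1). Table 4 agrees on the 14-day look-back. For these months it asks for no valid collection beforehand, and on repeats it adds: "Repeat collection, if necessary, is to be completed within ±14 days of dosing/visit".

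Two other places call for pre-dose sampling. Table 1 footnote a reads "All assessments are required to be performed prior to dosing at dosing visits, except for the PK 2-hour postdose sample collection and optional CT scan". Protocol 6.3 reads "On dosing days, all blood and urine samples will be collected prior to study drug administration".

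For PD and safety parameters, SAP 4.7 says that "no window rules will be implemented, and the reported eCRF visits will be used for analysis". SAP 2.5 counts 24-hour urinary oxalate among the PD data, so this governs the primary variable. Where a visit has several collections, SAP 4.1 uses the median of the valid ones. SAP 5.7.1.2 models Months 3, 4, 5 and 6, reports LS means for each visit, and takes the primary effect from the average of Months 4 to 6.

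**The concern.** Month 3 is the only scheduled urine measurement after one dose and before the second. A repeat is made because the first collection was invalid, so under SAP 4.1 the valid repeat becomes the Month 3 value. If it was collected after the second dose, it no longer describes the effect of one dose. Nothing in the SAP detects or removes it.

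The mirror case is a collection labelled Month 4 that was made before the second dose. Month 4 carries one third of the primary average.

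Any later decision to relabel or drop such samples would be made by a sponsor who, under SAP 2.5, is unblinded throughout. That is the main reason to settle the rule in advance, even though the numerical effect is small.

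**Working it through.** **The plan's own power figure.** Inputs from Protocol 7.1: 40 per group, SD 45%, difference 30%, two-sided 0.05. The standardised difference is 30 / (45 × √(2/40)) = 2.98. Power is 84.65% by normal approximation and 83.76% by noncentral t with 78 df. Table 7 states 84%, so the figure reproduces.

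**Windows (Tables 1 and 4).**
- Month 3 dose: 85 ± 14 = Day 71 to 99.
- Month 3 repeat, latest: 99 + 14 = Day 113.
- Month 4 visit: 113 ± 7 = Day 106 to 120. First collection: 106 − 14 = Day 92 to Day 120.

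**Month 3 repeat.** It can fall up to 14 days after the dose. At its latest (Day 113) it lies inside the Month 4 first-collection window (Day 92 to 120).

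**Month 4 before the dose.** The earliest collection against the latest in-window dose is 92 − 99 = −7 days. This needs a dose on Day 93 to 99 and a Month 4 visit on Day 106 to 112. There are 29 × 15 = 435 dose/visit pairs, of which 28 allow it. With 15 possible collection days per visit there are 435 × 15 = 6,525 combinations, of which 84 put the collection before the dose: 84/6,525 = 1.3%, assuming all days are equally likely. All 84 also lie within 14 days before dosing, so they fit the Month 3 window too.

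**Months 5 and 6.** The earliest collections are Day 134 − 14 = 120 and Day 155 − 14 = 141. These are 21 and 42 days after the latest in-window dose, so neither can precede it.

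**Effect on the primary contrast.** Suppose a share f of Month 4 samples loses a fraction r of the effect. The difference becomes 30 × (1 − f × r/3). The documents do not give r. If one dose shows 70–90% of the two-dose effect (assumption), r is 10–30%.

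| f | r | Difference | Power (normal approx.) |
|---|---|---|---|
| 0 | – | 30.00 | 84.65% |
| 1.3% | 10% | 29.99 | 84.6% |
| 1.3% | 30% | 29.96 | 84.6% |
| 25% | 30% | 29.25 | 82.8% |

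The last row treats every Month 4 sample taken less than 14 days after the dose (25% of combinations, including those before it) as if the second dose had not yet acted.

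**Effect on the Month 3 estimate.** The documents give no rate of invalid collections, so the share q of Month 3 values that are post-dose repeats is unknown. If q is 5–25% and each such value is shifted by 10–30% of a 30-point effect, that is 3 to 9 points (all assumptions). The Month 3 lumasiran-minus-placebo difference then moves by q × shift: from 0.05 × 3 = 0.15 to 0.25 × 9 = 2.25 points, in the direction of overstating the one-dose effect.

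**The case against.** Analysis by nominal visit is a common, prespecified choice. Footnote a speaks of dosing visits and Protocol 6.3 of dosing days, so a repeat made on a later day is not plainly forbidden by either. Month 3 lies outside the Months 4 to 6 contrast. A urine taken before the Month 3 dose would normally be recorded as Month 3. All of this stands, and it is why the point is about clear labelling and does not threaten the primary result. It does not remove the gap: Table 4 permits the late repeat, and the SAP then uses it as a Month 3 value.

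Four stronger readings are tempting, and the documents do not support them.

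- **That the urine windows run from Day 1.** Only visit days do. The Month 3 urine window is tied to dosing, and the late repeat arises from the +14 days in the repeat rule.
- **That pre-dose Month 4 samples materially dilute the primary endpoint.** The case is a corner of the windows, and the loss is 0.01 to 0.04 points on a difference of 30.
- **That Month 15 samples are confused with Month 6 samples**, undermining the stated aim that Month 9 dosing "will provide data to differentiate the effect of every 3 months and every 6 months dosing on urinary oxalate reduction". The allowed days since last dose do touch: 42 to 112 at Month 6 and 98 to 224 at Month 15. With uniform days, however, a Month 15 sample is closer to its dose than a Month 6 sample in only about 0.005% of simulated pairs. The central 95% ranges, about 53–101 and 116–206 days, do not overlap.
- **That Month 9 has the same post-dose problem.** Table 4 gives Month 9 no ±14-day repeat and requires one valid collection before dosing.

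**Conclusion.** The point holds as a gap between Table 4, Table 1 footnote a and SAP 4.7. A post-dose repeat can be analysed as the Month 3 value. It distorts the Month 3 by-visit estimate by an amount that depends on the unknown rate of invalid collections. It reaches the Months 4 to 6 contrast only indirectly, through the shared model.

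The opposite case, a Month 4 label on a sample taken up to 7 days before the second dose, is possible with every step in window. It arises in 1.3% of combinations if days are equally likely, and power stays at about 84.6%. A dose given outside its window under Protocol 5.2.2 would widen this overlap by an amount the documents do not let one estimate.

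The change is worth making because it is cheap, uses dates already recorded, and closes off relabelling after the data are seen. The primary result is not at risk.

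**What to change.** In SAP 4.7, add a rule for 24-hour urine:

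- A collection started after the actual Month 3 dose is not used as a Month 3 value.
- A collection started before the actual Month 3 dose is not used as a Month 4 value; it counts as Month 3.
- If the Month 3 dose was not given, the eCRF visit label stands.

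Report actual days since last dose alongside the Month 6, 9 and 15 summaries.

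In the protocol, reconcile the ±14-day repeat in Table 4 with the pre-dose requirement in Table 1 footnote a, so that sites work from one instruction.

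The cost is one SAP rule and one line in Table 4. Collection start and stop times (Protocol 6.2.1) and dose administration records (Protocol 5.2.6) already exist. A few Month 3 or Month 4 values become missing; SAP 4.3 already relies on the MMRM to use partial data without imputation. No dose timing changes.

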## **6.2.1.1.** Validity Criteria for 24-hour Urine Collections

Throughout the study, a urine collection will be considered valid if each of the following criteria are met:

- The collection is between 22 to 26 hours in duration between the initial discarded void and the last void or attempt to void.
- No voids are missed between the start and end time of the collection as indicated by the patient's urine collection diary.
- The 24-hour creatinine content is at least 10 mg/kg as assessed by the central laboratory.
- Patient complied with dietary recommendations appropriate for oxalate stone formers (detailed in the Dietary Reference Sheet) for the 4 days prior to the start of the urine collection and during the collection.

24-hour urine collections that are known to be invalid should still be submitted for analysis.

## 6.2.1.2. Variability Criterion for 24-hour Urine Collections at Screening

If the 2 valid 24-hour urine collections from screening meet eligibility requirements (both 24-hour urinary oxalate levels >ULN), the variability between the oxalate levels (in mg/day) should be assessed as follows:

$$Variability = \left| \frac{(Oxalate\ value\ \#1 - Oxalate\ value\ \#2)}{(Average\ of\ oxalate\ values\ \#1\ \&\ \#2)} \right| \times 100\%$$

If the variability is >20%, then an additional 24-hour urine collection should be obtained. The result of the additional sample will not impact the patient's eligibility for the study.

#### **6.2.2.** Kidney Stone Events

Since kidney stone events are recorded as an efficacy assessment, these events will not be captured as AEs or SAEs. However, if a patient experiences other AEs or SAEs during a kidney stone event, they should be reported as an AE (see Section 6.5.5.2).

Kidney stone events will be graded by the Investigator as mild, moderate, or severe as defined in Section 6.5.5.1. If there are changes in grade during an event, only the highest grade should be reported.

#### **6.2.2.1.** Clinical

All relevant clinical information pertaining to kidney stone events should be obtained, including laboratory values, medical records, discharge summaries, and medical test results (including stone composition, if available, and radiology reports). A clinical kidney stone event is defined as one of the following:

- Visible passage of a kidney stone
- A procedural intervention for removal of an asymptomatic or symptomatic stone (information on the location, number, and size of stones removed will be collected)

 Or, in the case of potential stone passages without visible stones, it will be up to the Investigator to evaluate patients' symptoms and determine whether a stone passage occurred or the symptoms were due to a different cause.

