# 2. OBJECTIVES AND ENDPOINTS

Objectives	Endpoints	
Primary		
To evaluate the effect of lumasiran on the percent change in urinary oxalate excretion	Percent change in 24-hour urinary oxalate from baseline to Month 6 (average across Months 4 through 6)	
Secondary		
• To evaluate the percentage of patients who achieve a ≥20% reduction in 24-hour urinary oxalate with lumasiran	Percentage of patients who achieve a ≥20% reduction in 24-hour urinary oxalate from baseline to Month 6 (average across Months 4 through 6)	
To evaluate the effect of lumasiran on urinary calcium oxalate supersaturation	Percent change in urinary calcium oxalate supersaturation from baseline to Month 6 (average across Months 4 through 6)	
Exploratory		

 
To evaluate the effect of lumasiran on absolute levels of urinary oxalate excretion
 
	Absolute change in 24-hour urinary oxalate from baseline to Month 6 (average across Months 4 through 6)	
To evaluate the effect of lumasiran on the occurrence of kidney stones	
 
Incidence rate of clinical and radiographic kidney stone events
 
Time to first kidney stone event
 
	
To evaluate additional PD parameters of plasma oxalate, plasma glycolate, and urinary glycolate	
 
Change from baseline in plasma oxalate
 
Change from baseline in plasma glycolate
 
Change from baseline in urinary glycolate
 
	
To characterize PK of lumasiran	Plasma PK of lumasiran	
To assess for antidrug antibodies (ADA) against lumasiran	ADA frequency and titer	
• To evaluate the effect of lumasiran on maintaining 24-hour urinary oxalate ≤upper limit of normal (ULN) over time	Percentage of patients with 24-hour urinary oxalate ≤ULN over time	
To evaluate the effect of lumasiran on maintaining a 25% reduction in urinary calcium oxalate supersaturation over time	Percentage of patients having a 25% reduction in urinary calcium oxalate supersaturation over time	
• To evaluate the effect of lumasiran on 24-hour urinary oxalate excretion after Month 6	Change from baseline in 24-hour urinary oxalate excretion after Month 6	

Objectives	Endpoints	
To evaluate the effect of lumasiran on estimated glomerular filtration rate (eGFR)	Change from baseline in eGFR	
To evaluate the effect of lumasiran on patient healthcare resource utilization	Kidney stone event related     hospitalizations, emergency room visits,     unscheduled office visits, or procedures	
Safety		

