5.7.3.1. Kidney Stone Events

CT scans for radiographic kidney stone events are read in pairs blinded to visit date (baseline and Month 15). All kidney stone-related analyses in this section will be done with all data collected.

A clinical kidney stone event is defined as one of the following:

- Visible passage of a kidney stone
- A procedural intervention for removal of an asymptomatic or symptomatic stone (information on the location, number, and size of stones removed will be collected)
- Or, in the case of potential stone passages without visible stones, it will be up to the Investigator to evaluate patients' symptoms and determine whether a stone passage occurred or the symptoms were due to a different cause.

A radiographic kidney stone event is defined as a kidney stone that is increased in size by $\geq 2 \text{ mm}$ in at least one dimension or a new stone ($\geq 1 \text{ mm}$ in size) observed on CT at Month 15 relative to baseline.

Time to first kidney stone event

Time to first event is defined as date of the first study drug to the first date of a kidney stone event. Censoring applies to patients who do not have a kidney stone event during the study. The follow-up time of these patients will be censored at the lost to follow-up date, study discontinuation, data cut-off date, or end of study, whichever occurs first.

Time to the first kidney stone event will be analyzed for a combination of both clinical and radiographic kidney stone events and for clinical kidney stone events separately for both the 6-month primary analysis period and the 15-month DB period (FA). All available data at the time of each database lock will be used. Kaplan-Meier estimator will be used to estimate the distribution of time to first kidney stone event in each treatment group. A log-rank test will be used to evaluate the treatment differences between each dose and the placebo. In addition, Cox proportional hazard regression will be performed to estimate the hazard ratio along with the 95% CI and p-value for each dose compared to the placebo. The model includes treatment, number of historical kidney stone events (>1 versus \leq 1) in the 12 months prior to screening.

Incidence rate of clinical and radiological kidney stone events

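### Stone removals already decided before the first dose count as on-study efficacy events, which pulls the exploratory stone-event ratios toward 1

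*Protocol*

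**What the plan says.** Protocol section 2 lists an exploratory objective, "To evaluate the effect of lumasiran on the occurrence of kidney stones", measured by the incidence rate of clinical and radiographic events and by time to first event.

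Protocol 6.2.2.1 gives three ways to have a clinical event:

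- a stone that the patient is seen to pass, with no condition on when it formed;
- a removal, worded as "A procedural intervention for removal of an asymptomatic or symptomatic stone (information on the location, number, and size of stones removed will be collected";
- symptoms without a visible stone, where "it will be up to the Investigator to evaluate patients' symptoms and determine whether a stone passage occurred".

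SAP 5.7.3.1 repeats these. Neither text requires the stone to be new or to have grown since baseline, and neither mentions procedures planned before dosing. The radiographic event differs: SAP 5.7.3.1 requires a new stone of at least 1 mm, or growth of at least 2 mm, "observed on CT at Month 15 relative to baseline".

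On the analysis side, "All kidney stone-related analyses in this section will be done with all data collected". The clock has no lag: "Time to first event is defined as date of the first study drug to the first date of a kidney stone event". On scope, "Time to the first kidney stone event will be analyzed for a combination of both clinical and radiographic kidney stone events". A second version takes the clinical events alone; the incidence rate is handled the same way. Every rate and time-to-first-event analysis therefore contains the clinical events as defined.

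**The concern.** The trial enrols recurrent stone formers. Inclusion criterion 2 accepts a new or enlarged stone on CT as a qualifying historical event, and that stone may still be in place at entry. No criterion in Protocol 4.1 or 4.2 specifically excludes a stone in place or a removal already booked.

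A patient can thus be randomised with a removal in the diary. When it takes place after Day 1 it is scored as an efficacy event. Lumasiran cannot have influenced the decision, so the event says nothing about the drug. In the time-to-first-event analysis it also uses up the patient's first event, so a later stone no longer counts there.

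At stake is the reading of the stone results. Protocol 3.2 gives collection of stone-event data as one reason for continuing to Month 15. A ratio pulled toward 1 could be taken as weak clinical effect when part of the shrinkage comes from the event definition. The 6-month analyses look most exposed: study CTs are at baseline and Month 15, or at an early-termination visit after Month 6, so events up to Month 6 are essentially all clinical. Protocol 3.3 predicts oxalate suppression close to steady state only at Month 6.

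**Working it through.** **The plan's own figure.** The documents state no event rate, effect size or power for stone events. The only power figure is for urinary oxalate: 40 per group, SD 45%, difference 30%, two-sided 0.05, power 84% (Protocol Table 7, SAP Table 1). The normal approximation gives 30 / (45 × √(2/40)) = 2.98, then Φ(2.98 − 1.96) = 0.8465; the noncentral t gives 0.8376. The figure reproduces, and this point does not touch it.

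**One unchanged stone, present at Day 1, under the written rules.**

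| What happens to it | Scored as |
|---|---|
| Left in place, seen again on CT at Month 15 | No event |
| Removed after Day 1, decided before Day 1 | Clinical event |
| Removed after Day 1, decided during the study | Clinical event |

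The second row is the gap: the outcome was settled before treatment.

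**Attenuation.** Let f be the share of placebo-arm events that are removals decided before dosing, and R the true ratio, lumasiran to placebo, for all other events. With the pre-decided removals equally frequent in both arms:

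observed ratio = f + (1 − f) × R, a shift of f × (1 − R) toward 1.

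| Assumed f | R = 0.50 | R = 0.70 |
|---|---|---|
| 0 | 0.50 | 0.70 |
| 0.20 | 0.20 + 0.80 × 0.50 = 0.60 | 0.20 + 0.80 × 0.70 = 0.76 |
| 0.25 | 0.625 | 0.775 |
| 0.50 | 0.75 | 0.85 |

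For rates this is exact in expectation. For hazards it holds when f is constant over follow-up; booked procedures are likely to cluster early, so the hazard ratio would also change with time.

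**Does excluding them help once their loss is counted?** Compare within one trial: 40 events in total, one dose against placebo at 1:1, R = 0.50, Schoenfeld power = Φ(√(d/4) × |ln HR| − 1.96).

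- f = 0.50. Per placebo event, the placebo arm has 0.50 pre-decided and 0.50 other; the lumasiran arm has 0.50 and 0.25. The total is 1.75, of which 0.75 are other events: 40 × 0.75 / 1.75 = 17.1. All 40 at HR 0.75: power 15%. The 17.1 alone at HR 0.50: power 30%.
- f = 0.25. The total is 1.625, of which 1.125 are other events: 40 × 1.125 / 1.625 = 27.7. All 40 at HR 0.625: power 32%. The 27.7 alone at HR 0.50: power 45%.

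Exclusion gains power despite the lost events, though power remains poor. Forty events all sensitive to treatment would give 59%, but that describes a different trial and is not what exclusion would recover. The values of f, R and 40 events are illustrations, not estimates.

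**The case against.** The strongest reply is that the endpoint is meant to capture clinical burden. Passage and removal are the same kinds of event used for eligibility and stratification, so counting all of them is coherent. The analyses are exploratory, carry no power claim, and are not part of any testing hierarchy. Randomisation is stratified by recent stone history and the Cox and negative binomial models adjust for it. Exclusion criterion 5 lets the Investigator keep out patients whose condition would interfere with interpreting the data. Medical records, radiology reports and the location, number and size of removed stones are collected, so planned procedures might be identifiable already.

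Much of this stands. It limits the consequence and argues for retaining the all-events analysis. It does not close the gap: stratification and adjustment do not remove drug-insensitive events from a numerator, criterion 5 is discretionary, and no analysis rule uses the information collected. The loss of a patient's first event applies only to time to first event; the rate analysis still counts later events.

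A reader might also infer that every passage or removal of a stone present at Day 1 is beyond lumasiran's reach. The documents do not support that. SAP 5.7.3.1 itself counts growth of an existing stone by at least 2 mm as an event, so the plan treats such stones as potentially modifiable, and slower growth could change whether a stone later passes or needs removal. The firm claim is confined to procedures decided before dosing.

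**Conclusion.** The gap is real and narrow. As written, removals decided before the first dose are scored as on-study efficacy events in every planned stone-event rate and time-to-first-event analysis, and they pull the ratios toward 1. The shift is f × (1 − R), and neither term is in the documents, so its size is unknown. Pre-decided removals are only a subset of events from stones already present, so f may be well below the larger values tabulated. The conclusion assumes that such procedures occur equally often in the arms, as randomisation gives on average, and that treatment does not materially change whether a booked removal goes ahead.

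Two further inferences would go too far. The expected effect is attenuation and lost power, not bias in favour of lumasiran. Nor do the stone analyses fail their objective altogether: the listed endpoint is clinical and radiographic events, and the radiographic component already refers to baseline. The primary oxalate conclusion is untouched.

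**What to change.** In Protocol 6.2.2.1 and SAP 5.7.3.1:

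1. For each removal procedure, record whether it was decided or scheduled before the first dose. The sponsor has access to unblinded data (Protocol 3.5, SAP 2.5), so blinded site staff or another blinded assessor should classify it from pre-dose records.
2. Exclude those procedures from the on-study event count. The patient stays at risk and keeps contributing person-time. List the excluded procedures by arm.
3. Keep the analysis of all events as a sensitivity analysis.
4. Optionally, among patients with a baseline CT, add a supportive analysis that omits clinical events matched to a baseline stone with no documented growth of 2 mm or more. Stones that grew must stay in, to agree with the radiographic definition. State that matching is uncertain once a stone has moved, impossible when no stone was seen, and limited to patients who chose CT.

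The cost is wording in two documents, slightly fewer events, and possibly one yes/no eCRF field; the eCRF is not among the documents, so an existing field may already serve.
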